1.4 Translational Objectives

- a. To evaluate genetic alterations, including low-frequency *KRAS* or *NRAS* mutations (definitive list of genes to be finalized after completion of enrollment based on latest scientific knowledge) as detected by high-depth sequencing as predictive biomarkers of efficacy.
- b. To evaluate PIK3CA pathway activation through PIK3CA mutations or PTEN protein loss as a predictive biomarker of innate resistance to this regimen.
- c. To evaluate gene expression signatures from screened patients with BRAF^{WT} and BRAF^{V600E} tumors.
- d. To provide validation of BRAF IHC using complementary sequencing methodology from screened patients with BRAF^{WT} and BRAF^{V600E} tumors.
- e. To confirm the estimated sensitivity of detectable BRAF V600E circulating cell-free DNA as a non-invasive biomarker for BRAF V600E mutation as detected by IHC in the primary tumor.
- f. To correlate radiographic tumor response with change in quantification of BRAF V600E alleles in circulating cell-free DNA.
- g. To monitor for known mechanism of acquired resistance to EGFR inhibition in circulating cell-free DNA.
- h. To assess the correlation of treatment efficacy between the patients and the matched patient-derived xenograft (PDX) models.
- i. To assess the correlation between PDX mechanisms for resistance and circulating free DNA (cfDNA) in plasma samples of matched patients following progression of disease.

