PDXs serve as biologically relevant models for studying metastatic cancer which utilize immunosuppressed mice that are subcutaneously implanted with biopsied human tumor specimens. (40,41) This model maintains a higher degree of intratumoral heterogeneity and incorporates human stroma from the implanted tumor that recapitulates a tumor microenvironment. In contrast, these attributes are not provided by tumor cells in culture or through homogenous cell-line derived xenografts. Additionally, the PDX platform also maintains slower doubling times for tumor growth and higher number of available molecular subtypes. These properties enable the use of PDXs as more realistic models to investigate novel therapies and resistance mechanisms for other types of malignancies. Prior work employing a PDX model of mCRC in a mock clinical trial comparing cetuximab with placebo showed similar outcomes to clinical trials in humans which had been run in an *unmatched* set of patients. (42-45) In addition, other retrospective series, in colorectal cancer and in other solid malignancies, have reported similarities in outcomes between patient responses to chemotherapy and tumor shrinkage in tumor xenografts. (46-48) However, the number of patients whose tumors were utilized was small and limits definitive conclusions to be made.

While these examples hint that the PDX model retrospectively may be promising to recapitulate responses in humans across various types of malignancies, thus far correlations in outcomes between the PDX model and the *matched* patient are poorly understood in *prospective* analyses. If a correlation between patient response on this study and a response in the matched PDX model is observed, then these findings may serve as the initial rationale for the design of future clinical trials for patients.

Inclusion of Women and Minorities

This study was designed to include women and minorities, but was not designed to measure differences of intervention effects. The anticipated accrual in the ethnicity/race and sex categories is shown in the table below.

Note: We estimate that approximately 440 patients will be screened for BRAF V600E mutation in order to enroll the 78 patients necessary for the study. This table represents only the patients with the BRAF mutation who register to Step 2 (randomization).

CLOSED EFFECTIVE 04/01/2010

Ethnic Category	Females	Males	Total
	Hispanic or Latino	3	3
Not Hispanic or Latino	44	55	99
Total Ethnic	47	58	105

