- h. To assess the correlation of treatment efficacy between patients and matched patient-derived xenograft (PDX) models.

The correlation between radiographic response in patients and reduction in tumor size in the corresponding PDX models receiving matched treatment will be assessed. Given a 67% success rate at MD Anderson in establishing PDXs using *BRAF*-mutated tumors, it is estimated that 12 PDXs will be established from the 18 tumor biopsies collected from either arm of **S1406**. For each PDX, 24 mice will be equally randomized into one of three arms: a control arm receiving placebo (C) or one of two treatment arms, irinotecan + cetuximab or irinotecan + vemurafenib + cetuximab. For each PDX, the mice will be assessed at Day 21. The average % reduction in tumor size will be compared between the mice receiving the treatment to which the corresponding patient had been randomized and the mice in the control arm receiving placebo. The treatment/ control ratio (%T/%C) will be calculated. To evaluate the association between the patient and corresponding xenograft model results, a Pearson correlation coefficient will then be estimated between %T/%C and the RECIST response of matched patients. 12 PDXs will have 80% power to detect a correlation coefficient of 0.712 at a two-sided 0.05 significance level.

In order to investigate further the correlation in raw tumor responses between the clinical and animal studies, a secondary analysis will model $\%T_{end}/T_{start}$ in the xenograft animals as a function of radiographic response according to RECIST criteria in matched patients via a linear mixed model.

- i. To assess the correlation between PDX mechanisms for resistance and circulating free DNA (cfDNA) in plasma samples of matched patients following progression of disease.

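### Objective 11.5h: one Pearson r pooled over both arms measures overall efficacy agreement, but cannot alone show that a PDX tracks its own patient; add an arm-adjusted partial correlation

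*Combined protocol and SAP*

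**What the plan says.** Section 1.4h gives the aim: "To assess the correlation of treatment efficacy between the patients and the matched patient-derived xenograft (PDX) models". Section 11.5h carries it out as follows.

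- Source of pairs: "12 PDXs will be established from the 18 tumor biopsies collected from either arm of" the trial.
- Mouse measure: 24 mice per PDX are split equally over placebo and the two regimens. %T/%C for a pair compares the "mice receiving the treatment to which the corresponding patient had been randomized and the mice in the control arm receiving placebo".
- Statistic: "a Pearson correlation coefficient will then be estimated between %T/%C and the RECIST response of matched patients".
- Power: "12 PDXs will have 80% power to detect a correlation coefficient of 0.712 at a two-sided 0.05 significance level".
- Secondary analysis: percent tumor size at end over start "in the xenograft animals as a function of radiographic response according to RECIST criteria in matched patients via a linear mixed model".

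No partial correlation, stratified correlation or within-arm analysis is named. That the arms are pooled is an inference, from the either-arm wording and from a power statement that uses all 12 PDXs.

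The PDX part of Section 2.0 gives the motivation: "thus far correlations in outcomes between the PDX model and the *matched* patient are poorly understood in *prospective* analyses". It adds that if a correlation is seen, "these findings may serve as the initial rationale for the design of future clinical trials for patients".

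**The concern.** Randomized arm fixes the regimen of the patient and also of the mice that enter that patient's %T/%C. A regimen effect can therefore move both variables. Dividing by placebo mice does not remove it, because the placebo group does not depend on the patient's arm.

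Pooled r thus mixes two things: agreement between a PDX and its own patient among patients on the same regimen, and any difference between the regimens that appears in both species. Section 2.0 gives reason to expect an effect in mice: earlier work saw regression in 10 of 10 mice with irinotecan plus BRAF and EGFR inhibition, and in 0 of 10 without BRAF inhibition. Section 11.2 plans for a doubling of median PFS in patients, from 2.4 to 4.8 months. Neither figure converts to a shift in %T/%C or in RECIST response.

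At stake is how the result is read. A significant pooled r could be taken as matching when it reflects a shared regimen effect. A non-significant one could be taken as no matching when a large mouse-only effect has diluted it.

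**Working it through.** **Inputs from Section 11.5h.** n = 12 pairs, two-sided alpha 0.05, target correlation 0.712, stated power 80%.

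**Assumptions (not in the documents).** A 6:6 arm split; bivariate normal data with unit SD within arm; RECIST response treated as continuous. Arm shifts are d_m in mice and d_p in patients, in within-arm SDs, both coded so that benefit has the same sign.

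**Step 1: the plan's own figure.** The critical |r| is t/√(t² + df). With 10 df, t = 2.228, so the critical value is 2.228/√(4.965 + 10) = 0.576. Simulating 12 pairs at a correlation of 0.712 with no arm effect gives 80.0% power. The stated 80% is correct for one homogeneous sample.

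**Step 2: what pooled r estimates.** With within-arm correlation ρ and q the product of the arm fractions (0.25 at 6:6):

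pooled r = (ρ + q·d_m·d_p) / √[(1 + q·d_m²)(1 + q·d_p²)]

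- ρ = 0, shifts 1/1: 0.25/1.25 = 0.20.
- ρ = 0, shifts 3/1: 0.75/√(3.25 × 1.25) = 0.37.
- ρ = 0, shifts 2/2: 1/2 = 0.50.
- ρ = 0.712, shifts 3/0: 0.712/√3.25 = 0.39.
- ρ = 0.712, shifts 1/1: (0.712 + 0.25)/1.25 = 0.77.

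**Step 3: how often each test is significant.** The comparator is the partial correlation adjusted for arm, with n − 3 = 9 df. Its critical value is 2.262/√(5.117 + 9) = 0.602. There were at least 200,000 simulated trials per scenario.

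| Shift, mouse/patient (SD) | Pooled, ρ = 0 | Pooled, ρ = 0.712 |
|---|---|---|
| 0/0 | 5% | 80% |
| 1/0 | 5% | 64% |
| 2/0 | 5% | 37% |
| 3/0 | 5% | 21% |
| 0.5/0.5 | 5.4% | 83% |
| 1/0.5 | 6.3% | 83% |
| 2/0.5 | 8.5% | 69% |
| 3/0.5 | 10% | 54% |
| 1/1 | 10% | 90% |
| 2/1 | 18% | 90% |
| 3/1 | 24% | 83% |
| 2/2 | 45% | 99% |

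In every row the arm-adjusted test gives about 5% at ρ = 0 and about 75.5% at ρ = 0.712. It reaches 80% at a within-arm correlation of about 0.735.

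**Step 4: uneven splits.** These are slightly milder. At 3/0.5 with ρ = 0, pooled r is significant in 9.2% (4:8) and 8.4% (3:9). At 3/0 with ρ = 0.712, pooled power is 23% (4:8) and 26% (3:9).

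**The case against.** The strongest reply is that pooled r answers the objective as worded. Section 1.4h asks about correlation of treatment efficacy, and a regimen effect seen in both species is part of that. If vemurafenib shrank the xenografts and did nothing in patients, a low pooled r would be the right answer. This stands, and it is why pooled r should stay. What it does not reach is the Section 2.0 gap, which contrasts matched with unmatched comparisons.

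A reader might infer four stronger things that the documents do not support.

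- **Inflated type I error.** The 10% to 45% figures are not false positives of the stated test, since the population pooled r is then truly non-zero (0.20 to 0.50). They are rates at which pooled r could be misread as matching.
- **A general loss of power from pooling.** The 64%, 37% and 21% figures assume exactly no patient effect, in a trial designed on a patient benefit. When both species shift comparably, pooled power is above the adjusted figure, partly because pooled r then also picks up the arm effect.
- **A demonstrated harm of a given size.** The documents give no SDs and no arm split. Sections 10.2 and 10.3 define response in categories, and Section 11.5h does not say whether percent change is used instead. If categories are correlated, the percentages above do not carry over.
- **A mixed model that leaves out treatment.** Its one-sentence description names only radiographic response and gives no other covariates or random effects. That is missing detail, not exclusion.

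It is also fair to say that the stakes are small: an optional substudy at six institutions, about 12 pairs, and no stated trial decision that rests on it.

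**Conclusion.** The point holds in a limited form. Pooled r is a sound summary of overall efficacy agreement, and its 80% power is computed correctly. It cannot by itself support a claim that a PDX tracks its own patient, because it does not separate that from a regimen effect common to both.

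The possible misreading as matching is negligible if either species has no arm effect or the shifts are small (5% to 6% at 0.5/0.5 or 1/0.5). It becomes material only at larger patient shifts (24% at 3/1, 45% at 2/2). Dilution of real matching occurs when the mouse shift far exceeds the patient shift (69% power at 2/0.5, 54% at 3/0.5, lower still with no patient effect). All of this rests on the assumed shifts, split and continuous normal response. This is a cheap improvement of low priority, confined to one translational objective. The primary PFS comparison is not touched.

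**What to change.** In Section 11.5h:

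1. Keep the pooled Pearson r, labelled as the measure of overall agreement in treatment efficacy.
2. Add the partial correlation between %T/%C and RECIST response, adjusted for randomized arm (9 df with 12 pairs). Make it the basis for any claim of matched PDX-patient concordance.
3. State its power: about 75% at a within-arm correlation of 0.712, and 80% at about 0.735.

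The cost is wording only. Arm is already known for every pair, and no new mice, patients or samples are needed. The price is one degree of freedom, a less favourable power figure (80% to about 75% at 0.712), and an assumption that the within-arm slope is the same in both arms, which about 12 pairs can hardly test.

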10.2 Objective Status at Each Disease Evaluation

Objective Status is to be recorded at each evaluation. All measurable lesions up to a maximum of 2 lesions per organ 5 lesions in total, representative of all involved organs, should be identified as *target* lesions at baseline. All other lesions (or sites of disease) including any measurable lesions over and above the 5 target lesions should be identified as *non-target* lesions. Measurements must be provided for target measurable lesions, while presence or absence must be noted for non-target measurable and non-measurable disease.

For studies that use disease progression as an endpoint, whole body scanning at specific intervals is necessary to determine that progression is NOT present outside of the "target" areas. Therefore, in these studies it is not acceptable to image only the "target" areas of the body in follow-up scans. For study-specific imaging requirements, see the Study Calendar in [Section 9.0](#).

- a. **Complete Response (CR):** Complete disappearance of all target and non-target lesions (with the exception of lymph nodes mentioned below). No new lesions. No disease related symptoms. Any lymph nodes (whether target or non-target) must have reduction in short axis to < 1.0 cm. All disease must be assessed using the same technique as baseline.
- b. **Partial Response (PR):** Applies only to patients with at least one measurable lesion. Greater than or equal to 30% decrease under baseline of the sum of appropriate diameters of all target measurable lesions. No unequivocal progression of non-measurable disease. No new lesions. All target measurable lesions must be assessed using the same techniques as baseline.
- c. **Stable:** Does not qualify for CR, PR, Progression or Symptomatic Deterioration. All target measurable lesions must be assessed using the same techniques as baseline.
- d. **Progression:** One or more of the following must occur: 20% increase in the sum of appropriate diameters of target measurable lesions over smallest sum observed (over baseline if no decrease during therapy) using the same techniques as baseline, as well as an absolute increase of at least 0.5 cm. Unequivocal progression of non-measurable disease in the opinion of the treating physician (an explanation must be provided). Appearance of any new lesion/site. Death due to disease without prior documentation of progression and without symptomatic deterioration (see [Section 10.2e](#)).

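### Section 11.5h defines neither side of the patient–PDX correlation: read literally, %T/%C is an unstable ratio of % reductions set against RECIST categories, and the stated 80% power holds only if both variables are roughly normal

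*Combined protocol and SAP*

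**What the plan says.** Section 11.5h (Translational Medicine, for objective 1.4h) expects 12 xenografts: "it is estimated that 12 PDXs will be established from the 18 tumor biopsies collected from either arm". In each, "For each PDX, 24 mice will be equally randomized into one of three arms": placebo, irinotecan plus cetuximab, or the triplet. Size is assessed at Day 21. Then "The average % reduction in tumor size will be compared between the mice receiving the treatment to which the corresponding patient had been randomized" and the placebo mice. The next step is a treatment/control ratio, written %T/%C with no formula, after which "a Pearson correlation coefficient will then be estimated between %T/%C and the RECIST response of matched patients". The power statement is "12 PDXs will have 80% power to detect a correlation coefficient of 0.712 at a two-sided 0.05 significance level".

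A secondary analysis models end size over starting size in the mice, by a linear mixed model, as a function of the patient's radiographic response by RECIST criteria.

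On the patient side, Section 10.2 defines complete response, partial response, stable and progression. Partial response, for instance, requires "Greater than or equal to 30% decrease under baseline of the sum of appropriate diameters of all target measurable lesions". Section 10.3 turns the sequence of statuses into a best-response category. No continuous RECIST response is defined, although Section 10.2 requires target-lesion measurements to be provided.

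**The concern.** Two things are undefined in a test that carries a stated power.

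**The mouse variable.** Since % reduction is the only quantity named, the literal %T/%C is mean % reduction on treatment divided by mean % reduction on placebo. A placebo tumor that grows has a negative % reduction, and one that hardly changes has a value near zero. The section has no rule for either case.

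**The patient variable.** Pearson correlation on three or four ordered codes discards the measured change in diameters, which is already recorded.

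With about 12 points, one PDX with a slow-growing placebo group can dominate r. A true patient–PDX match could be missed or a spurious one reported, and the scales could be chosen after the 12 points are seen. Section 2.0 presents an observed correlation as possible early support for designing later trials.

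**Working it through.** **Inputs from the documents (11.5h).** 18 biopsies × 0.67 take rate = 12.06, so 12 PDXs; 24 / 3 = 8 mice per group; r = 0.712; two-sided 0.05; 80% power.

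**Step 1: the plan's own figure.** With n = 12 and 10 degrees of freedom, t = 2.228. The critical |r| = t/√(10 + t²) = 2.228/√14.964 = 0.576. Power from the exact distribution of the sample correlation under bivariate normality at r = 0.712 is 0.8003. The stated figure reproduces for two jointly normal variables.

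**Step 2: can the literal ratio misorder PDXs?**

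| PDX | Treated reduction | Placebo change | Ratio of % reductions | Ratio of relative sizes |
|---|---|---|---|---|
| A | 60% | grew 200% | 60/(−200) = −0.3 | 0.40/3.00 = 0.13 |
| B | 20% | grew 10% | 20/(−10) = −2.0 | 0.80/1.10 = 0.73 |
| B, placebo shrinks instead | 20% | shrank 10% | 20/10 = +2.0 | 0.80/0.90 = 0.89 |

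For a fixed growing placebo, a better response gives a more negative ratio. B is therefore scored as the stronger response, although A shrank three times as much. A small change in placebo behavior moves B from −2.0 to +2.0. The ratio of relative sizes orders A and B correctly and stays positive.

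**Step 3: how much power could be lost?** The documents give no placebo growth, standard deviations or distribution of patient change, so everything below is assumed. Both models take n = 12, Pearson p < 0.05 and three RECIST levels cut at a 30% decrease and a 20% increase.

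*Model 1.* Correlation 0.712 between patient % change (mean −15, SD 35) and log relative-size T/C (median 0.5, log-SD 0.6).

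| Placebo relative size: median, log-SD | Continuous change, log T/C | Category, log T/C | Continuous change, ratio of % reductions | Category and ratio |
|---|---|---|---|---|
| 4.0, 0.3 | 0.80 | 0.67 | 0.72 | 0.60 |
| 2.5, 0.3 | 0.80 | 0.67 | 0.61 | 0.50 |
| 2.5, 0.5 | 0.80 | 0.67 | 0.33 | 0.28 |
| 2.0, 0.4 | 0.80 | 0.67 | 0.29 | 0.24 |

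Relative-size T/C without the log, against continuous patient change, gives 0.75.

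*Model 2.* Correlation 0.712 between treated % reduction (mean 0, SD 40) and patient shrinkage (mean 20, SD 35). C is the placebo % reduction. The last column is the share of PDX pairs ordered differently from their treated reduction.

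| C: mean, SD | Continuous change, ratio | Category and ratio | Pairs misordered |
|---|---|---|---|
| −200, constant | 0.80 | 0.66 | none |
| −200, 40 | 0.78 | 0.63 | 4% |
| −100, 40 | 0.61 | 0.49 | 8% |
| −50, 40 | 0.25 | 0.19 | 21% |
| −20, 30 | 0.14 | 0.10 | 34% |

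A negative denominator alone does no harm: with constant placebo growth the ratio only reverses sign, and two-sided power stays at 0.80. The damage comes from growth that varies between PDXs and approaches zero.

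**Step 4: the opposite case for categories.** If 0.712 is meant as the correlation with a three-level score itself, power is about 0.82 and categorization costs nothing.

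**The case against.** The strongest reply is that the literal reading may not be the intended one. The secondary analysis in 11.5h uses end over starting size. If T and C are relative sizes, %T/%C is always positive and close to what is proposed below. Likewise, % change is a plausible meaning of RECIST response: Section 2.0 reports the Phase I best response as a percentage, and the section chose Pearson here but logistic regression for RECIST assessment in 11.5f. This stands as a reason to call the problem an undefined variable rather than a demonstrated error. It does not remove the problem, because no formula or scale is stated and the only quantity named is % reduction.

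A reader might go further and infer that the stated 80% power is wrong or lost. The documents do not support that. The figure reproduces, it refers to a correlation whose scale is not specified, and the loss runs from none to nearly all depending on inputs the plan does not give. Model 1 also places r = 0.712 on the log T/C scale, so that measure reaches 80% by construction. If the true correlation is with treated-tumor size instead, log T/C itself has power of only 0.48 to 0.65 in the three placebo scenarios with medians of 2.0 and 2.5. The simulations show sensitivity to the definition; they do not show that one definition guarantees 80%.

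Finally, the secondary mixed model has no placebo denominator and gives some protection. It still uses RECIST criteria on the patient side.

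**Conclusion.** The concern holds in conditional form. Section 11.5h leaves both correlated variables undefined, and the literal reading of %T/%C can flip sign or misorder PDXs when placebo growth varies between them. The 80% power is right for two roughly bivariate-normal variables and should be tied to such variables.

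If 0.712 is a correlation on continuous scales, three categories alone bring power to about 0.65. Both choices read literally bring it to roughly 0.25 to 0.6, and lower still if placebo tumors barely grow. The ratio itself costs little or nothing if placebo growth is large and uniform. All of these figures rest on assumed growth and spread.

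The reach is limited: one translational objective, optional for patients, at the six institutions listed in Section 15.4. The primary PFS analysis is untouched. The correction is cheap enough to be worth making before the PDX data are analyzed.

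**What to change.** Amend 11.5h to state:

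- **Mouse variable.** Relative size = Day 21 size / starting size. T/C = mean relative size on the matched treatment divided by mean relative size on placebo, analyzed on the log scale.
- **Patient variable.** % change from baseline in the sum of target-lesion diameters, with the assessment time named in advance.
- **Early failures.** Add a Spearman analysis that ranks patients with early death, symptomatic deterioration, or new-lesion or non-target progression as worst. This matters: at the 2.4-month control median in Section 11.2, and assuming exponential times, 1 − 0.5^(1.84/2.4) = 41% of Arm 1 patients have a PFS event by 8 weeks (1.84 months). Some of these events are target-lesion growth with a usable % change, but others are not.
- **RECIST category.** Keep it as a descriptive display.
- **Power.** State that the 80% at r = 0.712 applies to the continuous measures in patients with measurable disease.

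The cost is a few sentences. The inputs are already collected through the tumor assessment forms and the mouse measurements. The downside is that patients without measurable disease (about 10%, from the 90% assumed measurable in Section 11.3) or without a follow-up scan have no % change. They enter only the rank or descriptive analysis, so fewer than 12 pairs may support the Pearson test.

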 1. This analysis will be very exploratory in nature. Analyzed gene signatures from tumor tissue will be described separately in patients with *BRAF*^{WT} (up to n=52, 90% of screen-negative patients) and *BRAF*^{V600E} (n=84, 90% of eligible patients). We will explore, but not limited to, associations between gene signatures and colorectal cancer oncogenesis, angiogenesis, immune pathways, PI3K, WNT, EGF, and MEK pathway signatures, epigenetic regulators, p53, NOTCH and TGF-beta signaling. The definitive list of genes and technologies might only be finalized after complete enrollment and will be based on scientific knowledge at that time.
- d. To provide validation of *BRAF* IHC using complementary sequencing methodology.
 1. Both *BRAF* and Cobas version 2.0 testing will be performed on screened patients (n=163). We will evaluate the sensitivity and specificity of *BRAF* IHC compared to the Cobas version 2.0 testing.

- e. To confirm the estimated sensitivity of detectable BRAF V600E circulating cell-free DNA as a non-invasive biomarker for BRAF V600E mutation as detected by IHC and Cobas in the primary tumor.
1. Unpublished results in 37 patients demonstrated 100% specificity and 78% sensitivity for the circulating cell-free DNA compared to the mutation assay on the primary tumor.
- f. To correlate radiographic tumor response with the change in quantification of BRAF V600E alleles in circulating cell-free DNA.
1. Analysis of plasma samples at baseline, during therapy, and at the time of progression across all arms (including Arm 3).
 2. No preliminary data are available for this aim.
 3. We will assess the relationship between RECIST radiographic assessment and change in BRAF V600E allele burden in the cfDNA via logistic regression.
- g. To monitor for known mechanism of acquired resistance to EGFR inhibition in circulating cell-free DNA (KRAS, NRAS mutations).
1. Analysis of plasma samples at baseline and at the time of progression on all arms (including progression on Arm 3).
 2. Preliminary data are not available for the BRAF population, but in a KRAS wild-type population, our preliminary data suggest that approximately 40% of patients develop new detectable mutations in KRAS, NRAS, or EGFR after treatment with cetuximab.
 3. Simple proportions with estimated 95% confidence intervals will be used to describe the observed incidence of new detectable mutations.

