cfDNA will be extracted from plasma taken from pre-treatment and post-progression samples of patients whose tumors were used to establish PDX models. These samples will then be analyzed by ultra-deep next-generation sequencing for the full exons of 15 genes (including KRAS, NRAS, EGFR, and MEK) and hotspot coverage for an additional 36 genes of interest. McNemar's test will be used to compare the mutation status of cfDNA before treatment and after progression for each gene of interest. We will adjust for multiple comparisons using methods described by Benjamin-Hochberg. (49) The concordance (i.e. proportion of the status unchanged, with 95% CI) of acquired mutation status between patient plasma samples and corresponding PDX models for each gene will be estimated. If concordance of PDX with matched patient in 6 of 12 pairs is observed, then the estimated half length of the 95% CI will be 0.25.

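### Section 11.5i: raw patient-PDX concordance counts shared absence of a mutation as agreement, so at low per-gene rates it can be high for an uninformative PDX

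*Combined protocol and SAP*

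**What the plan says.** Objective i in Section 1.4 is "To assess the correlation between PDX mechanisms for resistance and circulating free DNA (cfDNA) in plasma samples of matched patients" after progression. Section 11.5i carries it out. Plasma cfDNA from before treatment and after progression is sequenced for the "full exons of 15 genes (including KRAS, NRAS, EGFR, and MEK) and hotspot coverage for an additional 36 genes of interest", which makes 51 genes. The patient-PDX comparison is then "The concordance (i.e. proportion of the status unchanged, with 95% CI) of acquired mutation status between patient plasma samples and corresponding PDX models", estimated separately for each gene.

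On numbers, Section 11.5h states that "it is estimated that 12 PDXs will be established from the 18 tumor biopsies". Precision is illustrated by a single case, the one where "concordance of PDX with matched patient in 6 of 12 pairs is observed". For that case the section reports that "the estimated half length of the 95% CI will be 0.25".

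The only test named in 11.5i is McNemar's. It compares cfDNA before and after within the patient and does not address agreement between patient and PDX. The section gives no positive agreement, sensitivity, kappa or chance reference, and it does not restrict the comparison to genes in which a mutation appeared.

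The only acquired-mutation rate in the documents is in Section 11.5g: "approximately 40% of patients develop new detectable mutations in KRAS, NRAS, or EGFR after treatment with cetuximab". It comes from a KRAS wild-type population, and the same item says "Preliminary data are not available for the BRAF population".

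**The concern.** The objective asks whether the PDX develops the same resistance mechanism as the patient. That information lies in pairs where a mutation appears in at least one of the two sources. Acquired status for a gene is yes or no, so the proportion of pairs with matching status also credits every pair in which nothing happened. If new mutations in a given gene are uncommon, those empty pairs dominate and the proportion is high whatever the PDX does. A PDX that never acquires any mutation would also score well. What is at stake is how the PDX result is read: a list of genes with high concordance could be taken as support for the model when the data contain little or no evidence of it.

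**Working it through.** **Inputs.** Pairs: 12 (11.5h). Genes: 15 + 36 = 51 (11.5i). Combined acquired rate for KRAS, NRAS or EGFR: about 40% (11.5g, KRAS wild-type population). Per-gene rates for this population are not given. The rates below are assumptions, shown from 1% to 40%.

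**Step 1, the plan's own figure.** For 6/12 the Wilson half length is 1.96 × 0.5 / √(12 + 1.96²) = 0.98 / 3.98 = 0.246, which rounds to the stated 0.25. Other methods give 0.283 (Wald) and 0.289 (Clopper-Pearson). The figure stands; the interval method is not named.

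**Step 2, what the statistic counts.** For one gene, let a = pairs mutated in both sources, b = patient only, c = PDX only, d = neither. Raw concordance is (a + d)/12. Positive agreement with the patient as reference is a/(a + b). Only the second ignores d.

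**Step 3, expected concordance without information.** If the PDX acquires mutations independently at the same rate q, expected concordance is q² + (1 − q)². If the PDX never acquires one, it is 1 − q. Splitting the 40% equally and independently over three genes gives q = 1 − 0.6^(1/3) = 15.7%.

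| Rate q per gene | Independent PDX | Chance of at least 10/12 agreeing | PDX never mutates |
|---|---|---|---|
| 1% | 0.98 | 0.999 | 0.99 |
| 2% | 0.96 | 0.990 | 0.98 |
| 5% | 0.905 | 0.902 | 0.95 |
| 10% | 0.82 | 0.630 | 0.90 |
| 15.7% | 0.74 | 0.348 | 0.84 |
| 20% | 0.68 | 0.208 | 0.80 |
| 40% | 0.52 | 0.027 | 0.60 |

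The third column is for the independent PDX. Chance concordance is at least 0.90 for q up to 5.3% and at least 0.80 for q up to 11.3%.

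**Step 4, across the panel.** Take at least 10/12 as high concordance (my threshold; the plan sets none). Put KRAS, NRAS and EGFR at 15.7% and the other 48 genes at a common rate. The expected number of genes reaching the threshold with an independent PDX is 3 × 0.348 + 48 × the third column:

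- 1%: 1.04 + 47.95 = 49 of 51
- 2%: 1.04 + 47.5 = 49
- 5%: 1.04 + 43.3 = 44
- 10%: 1.04 + 30.2 = 31
- 15.7%: 51 × 0.348 = 18
- 20%: 1.04 + 10.0 = 11

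A rate of 10% already means 3 × 0.157 + 48 × 0.10 = 5.3 newly mutated genes per patient; 15.7% throughout means 51 × 0.157 = 8.0.

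**Step 5, what positive agreement would show.** Pooled over genes, its expected value with an independent PDX is about Σq²/Σq. With the other 48 genes at 5% this is (3 × 0.0245 + 48 × 0.0025)/(3 × 0.157 + 48 × 0.05) = 0.194/2.87 = 0.07. A simulation of 4,000 runs gave pooled positive agreement (symmetric form, 2a/(2a + b + c)) of 0.08, 0.06, 0.07 and 0.10 at 1%, 2%, 5% and 10%, beside mean raw concordance of 0.97, 0.95, 0.89 and 0.82.

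**Step 6, a single-gene example.** One patient acquires a mutation and a different patient's PDX acquires one. Raw concordance is 10/12 = 0.83. Positive agreement is 0/1, with an exact 95% interval of 0 to 0.975.

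**The case against.** The strongest objection is that low per-gene rates are not in the documents. The one available figure points the other way for the genes that matter most: at 15.7% each, KRAS, NRAS and EGFR have chance concordance of 0.74, and a single gene carrying the whole 40% would have 0.52. A reader might infer that most of the 51 genes will look highly concordant whatever happens. The documents do not support that. With an independent PDX it holds up to roughly 10% per gene and fails near 15% and above.

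A reader might also infer that following the plan would lead to a claim that the PDX works. That does not follow either. Section 11.5i only estimates concordance with an interval. It sets no success threshold and no test of agreement, and its illustration is 6 of 12, not a value near 1. The before-and-after cfDNA analysis should also show which genes had no new mutation in any patient. This is a partial safeguard, because it says nothing about the PDX and no 2x2 counts are promised.

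The remedy has limits too. In the same simulation, on average 38, 29, 14 or 4 of the 51 genes (other genes at 1%, 2%, 5% or 10%) had no mutation in either source, so per-gene kappa or positive agreement cannot be estimated there.

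These points limit the size of the concern and shape the fix. They do not remove the defect: nothing in the section separates shared presence from shared absence.

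**Conclusion.** The concern holds in conditional form. Raw concordance in Section 11.5i credits pairs with no acquired mutation in either source, so on its own it does not answer objective 1.4i. If per-gene rates are about 10% or lower, an uninformative PDX would be expected to reach at least 10/12 agreement in about 31 to 49 of the 51 genes. This rests on three assumptions: the rates themselves, a PDX that mutates independently at the patient's rate, and 10/12 as the mark of high concordance. For KRAS, NRAS and EGFR the inflation is smaller, about 0.74 under the equal, independent split. The stated half length of 0.25 is not in dispute.

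The consequence is minor. This is the last of nine translational objectives, in an optional sub-study at six institutions (Section 15.4) with about 12 PDXs. No primary or secondary analysis depends on it.

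**What to change.** Keep raw concordance and add the following to Section 11.5i:

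- For each gene with at least one acquired mutation in either source, give the 2x2 counts and the positive and negative agreement, with patient plasma as reference and exact 95% intervals. Where no patient acquired a mutation in that gene, positive agreement has no denominator and the counts alone are shown.
- State how many genes had no acquired mutation in either source, so that their perfect concordance is not read as evidence.
- Give one positive agreement pooled over genes, with an interval clustered by patient-PDX pair, for example a bootstrap over pairs. Results for different genes come from the same 12 or so pairs and are not independent.
- Treat kappa as optional, and report it only where it can be estimated.

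This would match Section 11.5d, which already uses sensitivity and specificity for the BRAF assay comparison. It needs no new samples or assays. The costs are very wide intervals with about 12 pairs and a set of displayed genes that depends on the data; the report should state both.
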